3.2 Exclusion Criteria (none of the following may be present for enrollment)

- 3.2.1 Clinical picture indicative of leukostasis or evidence of disseminated intravascular coagulopathy.
- 3.2.2 Uncontrolled coagulopathy or bleeding disorder.
- 3.2.3 Systemic antineoplastic therapy or radiotherapy for other malignant conditions within 14 days before the first dose of any study drug, except for hydroxyurea.
- 3.2.4 Uncontrolled high blood pressure (*i.e.*, systolic blood pressure >180 mm Hg, diastolic blood pressure >95 mm Hg).

- 3.2.5 Female patients who intend to donate eggs (ova) during the course of this study or 4 months after receiving their last dose of study drug(s).
- 3.2.6 Male patients who intend to donate sperm during the course of this study or 4 months after receiving their last dose of study drug(s).
- 3.2.7 Ongoing toxicities \geq grade 2 from prior therapy, except those related to hydroxyurea (which is permitted through the first 5 days of study treatment).
- 3.2.8 APL (M3).
- 3.2.9 Active central nervous system (CNS) leukemia.
- 3.2.10 History of allergic reactions attributed to compounds of similar chemical or biologic composition to MLN4924 (pevonedistat) or belinostat.
- 3.2.11 Stem cell transplant within previous 3 months prior to initiation of study therapy.
- 3.2.12 Major surgical procedures \leq 28 days before beginning study treatment or minor surgical procedures \leq 7 days before beginning study treatment. No waiting required after placement of a vascular access device.
- 3.2.13 Uncontrolled intercurrent illness or infection.
- 3.2.14 Circulating blast count $>50,000 \text{ mm}^3$ within 7 days preceding enrollment.
- 3.2.15 Current candidacy for a potentially curative allogenic stem cell transplant, unless declined.
- 3.2.16 Left ventricular ejection fraction (LVEF) $<50\%$ as assessed by echocardiogram or radionuclide angiography.
- 3.2.17 Prolongation of the heart-rate corrected QT (QTc) interval $\geq 450 \text{ ms}$ (*i.e.*, grade 1 or higher) on electrocardiogram (ECG) prior to initiation of study treatment.
 - If baseline QTc on screening ECG is $\geq 450 \text{ ms}$ (*i.e.*, grade 1 or higher):
 - Check potassium and magnesium serum levels, and
 - Correct any identified hypokalemia and/or hypomagnesemia and repeat ECG to confirm QTc interval.

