Myeloid growth factors (e.g. , G-CSF, GM-CSF)	In general, the use of myeloid growth factors is discouraged and should be restricted. For patients in CR, CRi, or marrow CR, growth factors may be used in specific circumstances after discussion with the project clinician or designee. Use of growth factors may also be used in patients with grade 3 or grade 4 febrile neutropenia after discussion and agreement with the principal investigator or designee. Additionally, to avoid dose delays, patients who experience grade 4 neutropenia (ANC <500/mcL) with or without fever in Cycle 2 or later may receive granulocyte colony-stimulating factor (G-CSF) or granulocyte macrophage colony-stimulating factor (GM-CSF) between days 28-42 after discussion and agreement with the principal investigator (or designee).
Platelet transfusion	Permitted as medically necessary per institutional guidelines.
Red blood cell transfusion	Permitted as medically necessary per institutional guidelines.

G-CSF=granulocyte colony-stimulating factor, GM-CSF=granulocyte macrophage colony-stimulating factor, CR=complete response, CRi=complete remission with incomplete blood count recovery, ANC=absolute neutrophil count.

Supportive Care Guidelines

Condition	Recommendation

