12.1 Hematologic Tumors

Treatment responses will be classified according to the IWG revised criteria for response assessment in AML (Cheson *et al.*, 2003); the ELN recommendations for diagnosis and management of AML (Dohner *et al.*, 2010); and the IWG application and proposal for modification of response criteria in MDS (Cheson *et al.*, 2006).

Bone marrow blast percentages will be defined by manual differential count on the aspirate.

Morphologic complete remission (CR): <5% bone marrow blasts and no blasts with Auer rods with no requirement for bone marrow cellularity, as long as absolute neutrophil count (ANC) $\geq 1000/\text{mcL}$ AND platelets $\geq 100,000/\text{mcL}$, patient is transfusion-independent, and has no residual evidence of extramedullary leukemia. Persistent dysplasia is allowed.

Morphologic complete remission with incomplete blood count recovery (CRi): All criteria for morphologic CR must be met, except that the patient has residual neutropenia (ANC $< 1000/\text{mcL}$) or thrombocytopenia (platelets $< 100,000/\text{mcL}$).

Morphologic leukemia-free state (MLFS): <5% bone marrow blasts, no blasts with Auer rods, and no persistent extramedullary leukemia, peripheral blood count recovery not required.

Cytogenetic complete remission (CRc): There should be no evidence of a previously present cytogenetic abnormality (*e.g.*, t(8;21), inv 16, t(9;22), *etc.*) by conventional karyotyping or Fluorescent in situ hybridization (FISH) (must be specified).

Molecular complete remission (CRm): There should be no evidence of a previously present molecular abnormality (*e.g.*, BCR-ABL, mutated FLT3, NPM1, or CEBPA, *etc.*). The sensitivity of the PCR assay must be specified.

Partial remission (PR): All peripheral blood criteria for CR must be met, with a decrease of at least 50% in the percentage of blasts to 5% to 24% in the bone marrow aspirate. A value of <5% bone marrow blasts will be considered a PR if Auer rods are present.

Stable disease (SD): Patients not meeting criteria for CR, CRi, ML-FS, CRc, CRm, PR, relapse, or progressive disease.

Morphologic relapse: Relapse after CR is defined as reappearance of leukemic blasts in the

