peripheral blood or $\geq 5\%$ blasts in the bone marrow not attributable to any other cause (*e.g.*, bone marrow regeneration). Relapse from PR is defined as $\geq 25\%$ bone marrow blasts not attributable to bone marrow regeneration or use of colony stimulating factors. The appearance of new dysplastic changes should also be considered relapse.

Progressive Disease: Any of the following in patients who have not previously met CR, CRi, CRc, CRm, ML-FS, or PR criteria while on study therapy:

- $\geq 50\%$ increase in the bone marrow blasts (by aspirate differential count) over the best previous assessment (comparing to a minimum bone marrow blast percentage threshold of 20% at baseline or during study at such time as that threshold is met).
- $\geq 50\%$ increase in peripheral blood absolute blast count over the best previous assessment (comparing to a minimum peripheral blood absolute blast count threshold of $\geq 1000/\text{mL}$ at baseline or during study at such time as that threshold is met). In some cases, the peripheral blood absolute blast count may not accurately reflect disease burden, especially with targeted therapies. At investigator discretion, the patient can continue on study with close monitoring of peripheral blood absolute blast count and bone marrow biopsies to assess bone marrow blast percentage (by aspirate differential count) as clinically indicated.
- Development of new extramedullary disease.

Appearance of new dysplastic changes should be closely monitored for emerging relapse. In a patient who has been recently treated, dysplasia or a transient increase in blasts may reflect a chemotherapy effect and recovery of hematopoiesis. Cytogenetics should be tested to distinguish true relapse from therapy-related MDS/AML.

Duration of remission is defined only for patients who achieve CR, CRi, CRc, or CRm and is measured by the interval from the date of CR (by blood count recovery and BM examination), until the date of relapse.

Cytogenetic responses: For patients with AML or MDS, a complete cytogenetic response requires the disappearance of a previously present cytogenetic abnormality (without appearance of new ones), while a partial cytogenetic response requires a $\geq 50\%$ reduction in the number of metaphases positive for the chromosomal abnormality by conventional karyotyping.

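### The peripheral-blast floor for progressive disease in Section 12.1 is written per mL, which makes it 1 blast/mcL and practically non-binding; the unit needs reconciling with the other blood counts

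*Combined protocol and SAP*

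**What the plan says.** Section 12.1, Progressive Disease, applies to patients who have not yet met a response category on study therapy. Its second bullet requires a rise of at least 50%, described as an "increase in peripheral blood absolute blast count over the best previous assessment". The rise is judged against a minimum: "comparing to a minimum peripheral blood absolute blast count threshold of" at least "1000/\text{mL}$ at baseline or during study at such time as that threshold is met". The parallel marrow bullet also has a minimum: "comparing to a minimum bone marrow blast percentage threshold of 20% at baseline or during study".

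The other blood-count thresholds use a different scale:

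- Section 12.1, CR and CRi: neutrophils and platelets per mcL, for example "thrombocytopenia (platelets $< 100,000/\text{mcL".
- Section 6.5.1, myeloid growth factors: "grade 4 neutropenia (ANC <500/mcL) with or without fever".
- Section 3.2.14, the same analyte at eligibility: "Circulating blast count $>50,000 \text{ mm}^3$ within 7 days preceding enrollment".
- Section 3.1.5: CD4 count in cells per mm³.

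Two clauses bear on the consequence. The peripheral-blast bullet lets the investigator keep a patient on study, with monitoring, when the peripheral count may not reflect disease burden. Section 6.7 lists progression as a reason to stop treatment, but allows patients with progression to remain after discussion with the principal investigator.

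**The concern.** A minimum count in a relative-change criterion keeps small fluctuations at low counts from being labelled progression. The marrow minimum of 20% can do that job. A peripheral minimum of 1/mcL hardly can, because almost any blast seen on a differential exceeds it. The peripheral criterion then becomes, in practice, a bare 50% relative rise from a low and imprecise count.

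Stable disease in Section 12.1 is the residual category, so a looser progression rule takes patients out of it. Progression is a listed reason to stop treatment (Section 6.7). Patients who discontinue with stable disease enter the two-year follow-up, whereas progression is not among the qualifying categories (Section 6.8; Section 11, footnote e).

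**Working it through.** **Inputs from the protocol.** Floor 1000/mL; relative rise at least 50% over the best previous assessment (both Section 12.1). The floor is a stated threshold and is not derived from other figures, so there is no plan calculation to reproduce.

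**Step 1: unit conversion.** 1 mL = 1000 mcL, so 1000/mL ÷ 1000 = 1/mcL. Since 1 mm³ = 1 mcL, the eligibility counts are on the same scale as the mcL counts. Per-mL figures elsewhere describe laboratory cell suspensions, not blood counts.

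**Step 2: what qualifies.** A rise from 10 to 15/mcL is 10,000 to 15,000/mL. Both values exceed 1000/mL, and (15 − 10)/10 = 50%, so the criterion is met as written. If the unit were per mcL, the lowest qualifying count would be 1.5 × 1000 = 1500/mcL.

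**Step 3: when the written floor binds.** Assumption, not in the protocol: a differential of 100 or 200 cells. The smallest non-zero blast count is the white count divided by the cells counted.

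| White count (/mcL) | One blast, 200 cells (/mcL) | One blast, 100 cells (/mcL) | Blast share equal to 1000/mcL |
|---|---|---|---|
| 100 | 0.5 | 1 | not reachable |
| 1,000 | 5 | 10 | 100% |
| 2,000 | 10 | 20 | 50% |
| 5,000 | 25 | 50 | 20% |
| 10,000 | 50 | 100 | 10% |

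One blast falls below 1/mcL only at a white count under 100/mcL (100 cells) or under 200/mcL (200 cells). Otherwise the floor excludes only a reference count of zero.

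**Step 4: counting noise.** Take two independent differentials of n cells, with an unchanged true blast share p and an unchanged white count. Let a and b be the blasts counted, each binomial(n, p). The chance of a spurious qualifying rise is the sum of P(a) × P(b ≥ 1.5a) over all a ≥ 1 for which the first count reaches the floor. With the floor at 1/mcL and white counts from 1,000 to 10,000/mcL:

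| True blast share | n = 100 | n = 200 |
|---|---|---|
| 1% | 0.113 | 0.260 |
| 2% | 0.261 | 0.302 |
| 5% | 0.283 | 0.197 |
| 10% | 0.191 | 0.100 |
| 20% | 0.087 | 0.025 |
| 50% | 0.003 | 0.000 |

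With a floor of 1000/mcL, the same probability is 0.0000 to four decimals at every true count examined from 10 to 500/mcL. At higher counts the floor removes less: at 2000/mcL (20% of 10,000) the probability is 0.0845 with 100 cells and 0.0251 with 200, almost as without it. These are single comparisons. The rule uses the best previous assessment, so taking the lowest of several earlier counts would push the figures up.

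**The case against.** The strongest objection is that the point turns on one letter in text converted from PDF. The unit in Section 3.2.14 also looks damaged, since it lacks a slash, and the protocol mixes mm³ and mcL. A misread mcL therefore cannot be excluded. Against that, mcL appears intact four times in the CR and CRi definitions of the same section. The uncertainty stands, and is why a source check comes first.

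The second objection is that little depends on it, and much of this stands. The primary endpoint is the RP2D, driven by Cycle 1 DLTs. All analyses are descriptive. The investigator-discretion clause and Section 6.7 both allow treatment to continue, and Section 12.1 itself warns that a transient blast rise may be a treatment effect. These provisions soften the effect on treatment but leave the written classification unchanged, and case-by-case discretion may be used differently across sites.

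A reader might infer three stronger things that the documents do not support:

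- **That the floor never operates.** It still excludes a zero reference count, and it can bind at very low white counts.
- **That the response rate is wrong.** Section 9.3.3 codes stable disease and progression alike as non-response. Only an indirect effect remains, if early removal prevents a later response.
- **That duration of response is shortened.** The bullet applies only to patients without a prior response.

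**Conclusion.** The unit is inconsistent with the rest of the protocol by a factor of 1000. As written, the floor is practically non-binding. Under the assumed 100- or 200-cell differential and an unchanged blast share, counting noise alone meets the criterion with probability 0.11–0.30 per comparison at 1–5% blasts, 0.10–0.19 at 10% and 0.03–0.09 at 20%.

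The consequence is confined to the stable-disease versus progression label in patients without a prior response, time on treatment, and entry to long-term follow-up. The RP2D, duration of response and direct responder coding are untouched. The point should be corrected because it concerns a decision threshold and is cheap to settle. It is conditional on the source text reading per mL. All per-mcL figures above illustrate that unit; they do not establish what the sponsor intended.

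**What to change.** Check the source text of the peripheral-blast bullet. If it reads per mL:

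- reconcile the unit with the CR and CRi limits in Section 12.1, the neutrophil limit in Section 6.5.1 and the circulating-blast limit in Section 3.2.14;
- have the sponsor confirm the intended threshold, since progression is a reason to stop treatment and this review does not choose the value;
- align any CRF field that carries the threshold (no CRF is in the documents, so whether one does is unknown);
- re-check any progression already called on this criterion alone.

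The cost is one unit in the protocol, possibly one CRF field, and a small retrospective check. Section 9.2 caps enrolment at 45, and only patients without a prior response are concerned. If the source already reads per mcL, nothing needs changing.

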13. STUDY OVERSIGHT AND DATA REPORTING / REGULATORY REQUIREMENTS

AE lists, guidelines, and instructions for AE reporting can be found in Section 10 (Adverse Events: List and Reporting Requirements).

13.1 Study Oversight

This protocol is monitored at several levels, as described in this section. The Protocol Principal Investigator is responsible for monitoring the conduct and progress of the clinical trial, including the ongoing review of accrual, patient-specific clinical and laboratory data, and routine and

SAEs; reporting of expedited AEs; and accumulation of reported adverse events from other trials testing the same drug(s). The Protocol Principal Investigator and statistician have access to the data at all times through the CTMS web-based reporting portal.

For the phase 1 portion of this study, all decisions regarding dose escalation/expansion/de-escalation require sign-off by the Protocol Principal Investigator through the CTMS/IWRS. In addition, for the Phase 1 portion, the Protocol Principal Investigator will have at least monthly, or more frequently, conference calls with the Study Investigators and the CTEP Medical Officer(s) to review accrual, progress, and adverse events and unanticipated problems.

All Study Investigators at participating sites who register/enroll patients on a given protocol are responsible for timely submission of data via Medidata Rave and timely reporting of adverse events for that particular study. This includes timely review of data collected on the electronic CRFs submitted via Medidata Rave.

All studies are also reviewed in accordance with the enrolling institution's data safety monitoring plan.

13.2 Data Reporting

Medidata Rave is a clinical data management system being used for data collection for this trial/study. Access to the trial in Rave is controlled through the CTEP-IAM system and role assignments.

Requirements to access Rave via iMedidata:

- A valid account, and
- Assigned a Rave role on the LPO or PO roster at the enrolling site of: Rave CRA, Rave Read Only, Rave CRA (LabAdmin), Rave SLA, or Rave Investigator.
Rave role requirements:
 - Rave CRA or Rave CRA (Lab Admin) role, must have a minimum of an Associate Plus (AP) registration type,
 - Rave Investigator role, must be registered as an Non-Physician Investigator (NPIVR) or Investigator (IVR), and
 - Rave Read Only role, site staff must have at a minimum an Associates (A) registration type.
- [REDACTED] for registration types and documentation required.

Upon initial site registration approval for the study in Regulatory Support System (RSS), all persons with Rave roles assigned on the appropriate roster will be sent a study invitation e-mail from iMedidata. To accept the invitation, site staff must log in to the Select Login [REDACTED] g their CTEP-IAM username and password, and click on the *accept* link in the upper right-corner of the iMedidata page. Site staff will not be able to access the study in Rave until all required Medidata and study specific trainings are completed. Trainings will be in the form of electronic learnings (eLearnings), and can be

accessed by clicking on the link in the upper right pane of the iMedidata screen. If an eLearning is required and has not yet been taken, the link to the eLearning will appear under the study name in iMedidata instead of the *Rave EDC* link; once the successful completion of the eLearning has been recorded, access to the study in Rave will be granted, and a *Rave EDC* link will display under the study name.

Site staff that have not previously activated their iMedidata/Rave account at the time of initial site registration approval for the study in RSS will receive a separate invitation from iMedidata to activate their account. Account activation instructions are located on the CTSU website in the Data Management section under the Rave resource materials (Medidata Account Activation and Study Invitation Acceptance). Additional information on iMedidata/Rave is available on the

13.2.1 Method

This study will be monitored by the CTMS. Data will be submitted to CTMS at least once every two weeks via Medidata Rave (or other modality if approved by CTEP). Information on CTMS reporting is available at

13.2.2 Responsibility for Data Submission

For ETCTN trials, it is the responsibility of the Principal Investigator(s) at the site to ensure that all investigators at the ETCTN Sites understand the procedures for data submission for each ETCTN protocol and that protocol specified data are submitted accurately and in a timely manner to the CTMS via the electronic data capture system, Medidata Rave.

Data are to be submitted via Medidata Rave to CTMS on a real-time basis, but no less than once every 2 weeks. The timeliness of data submissions and timeliness in resolving data queries will be tracked by CTMS. Metrics for timeliness will be followed and assessed on a quarterly basis. For the purpose of Institutional Performance Monitoring, data will be considered delinquent if it is greater than 4 weeks past due.

Data from Medidata Rave and CTEP-AERS is reviewed by the CTMS on an ongoing basis as data is received. Queries will be issued by CTMS directly within Rave. The queries will appear on the Task Summary Tab within Rave for the CRA at the ETCTN to resolve. Monthly web-based reports are posted for review by the Drug Monitors in the IDB, CTEP. Onsite audits will be conducted by the CTMS to ensure compliance with regulatory requirements, GCP, and NCI policies and procedures with the overarching goal of ensuring the integrity of data generated from NCI-sponsored clinical trials, as described in the ETCTN Program Guidelines, which may be found on the CTEP

and

CTSU websites.

[REDACTED] Customized eCRFs will be included when appropriate to meet unique study requirements. The Principal Investigator is encouraged to review the eCRFs, working closely with CTMS to ensure prospectively that all required items are appropriately captured in the eCRFs prior to study activation. CTMS will prepare the eCRFs with built-in edit checks to the extent possible to promote data integrity.

CDUS data submissions for ETCTN trials activated after March 1, 2014, will be carried out by the CTMS contractor, Theradex. CDUS submissions are performed by Theradex on a monthly basis. The trial's lead institution is responsible for timely submission to CTMS via Rave, as above.

Further information on data submission procedures can be found in the ETCTN Program Guidelines

[REDACTED] Quality Portal (DQP) provides a central location for site staff to manage unanswered queries and form delinquencies, monitor data quality and timeliness, generate reports, and review metrics.

The DQP is located on the CTSU members' website under Data Management. The Rave Home section displays a table providing summary counts of Total Delinquencies and Total Queries. DQP Queries, DQP Delinquent Forms, and the DQP Reports modules are available to access details and reports of unanswered queries, delinquent forms, and timeliness reports. Review the DQP modules on a regular basis to manage specified queries and delinquent forms.

The DQP is accessible by site staff that are rostered to a site and have access to the CTSU website. Staff that have Rave study access can access the Rave study data using a direct link on the DQP.

To learn more about DQP use and access, click on the Help icon displayed on the Rave Home, DQP Queries, and DQP Delinquent Forms modules.

Note: Some Rave protocols may not have delinquent form details or reports specified on the DQP. A protocol must have the Calendar functionality implemented in Rave by the Lead Protocol Organization (LPO) for delinquent form details and reports to be available on the DQP. Site staff should contact the LPO Data Manager for their protocol regarding questions about Rave Calendaring functionality.

